### 7.3.1 Criteria for Response Assessment

Modified IWG 2003 Response Criteria (Table 1) will be used by an independent blinded central reader to identify AML subjects with CR, CRp, CRi, or partial response (PR) for further statistical analyses.

**Table 1: Modified 2003 IWG AML Response Criteria**

Response a	Peripheral Blood (PB)	Bone Marrow (BM)
CR	ANC $\geq$ 1000/ $\mu$ L, Platelets $\geq$ 100,000/ $\mu$ L, independence from RBC and platelet transfusions over the past week, no leukemic blasts b	<5% leukemic blasts
CRp	ANC $\geq$ 1000/ $\mu$ L, Platelets <100,000/ $\mu$ L, independence from RBC transfusions over the past week, no leukemic blasts b	<5% leukemic blasts
CRi	ANC <1000/ $\mu$ L, no leukemic blasts b	<5% leukemic blasts
PR	ANC $\geq$ 1000/ $\mu$ L, Platelets $\geq$ 100,000/ $\mu$ L, no leukemic blasts b	Decrease of $\geq$ 50% in leukemic blasts to level of 5% to 25%

a Responses are based on both PB and BM conditions.

b For the purpose of response assessment and according to published IWG criteria, blasts may be seen in PB as rare PB blasts may be identified during regeneration, but the subject is in CR if BM blasts are <5% with no Auer rods (Cheson et al 2003).

ANC=absolute neutrophil count; CR=complete response; CRp=complete response with incomplete platelet recovery; CRi=CR with incomplete blood count recovery; PR=partial response.

Source: [Cheson et al 2003](#)

Subjects with these different response categories, as well as nonresponders (NR) and nonevaluable (NE) subjects will be listed and summarized using frequency counts and proportion of subjects with each category of best response. Subjects who did not have a valid post-treatment efficacy assessment (ie, no post-treatment BM/PB sample or the quality of BM/PB sample is not adequate for the central pathologist to provide an assessment of efficacy) will be classified as NE for response classifications. These subjects will be included in the denominator of the ITT analysis for calculation of different response rates. Subjects who cannot be classified into a response category (CR, CRp, CRi, PR) or the NE category will be classified as NR.

In particular, the best response in the order of CR, CRp, CRi and PR will be used when a subject experienced different response levels at different visits. Subjects who progressed (see Section 7.3.6 for definition) without first having a response (CR, CRp, CRi, or PR) will be included in the NR category for summary purpose.

Response rate based on the central reader's assessments will be calculated for the best response categories described below to assess overall efficacy observed.

- CR, CRp, CRi, PR.
- Composite CR ( $CR_c = CR + CR_p + CR_i$ ).

Investigators will also provide the assessment of response using the same Modified IWG 2003 Response Criteria (Table 1). However, their assessments will only be provided in a data listing.

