9.2 Efficacy

PB will be assessed at screening and on Day 1 of each cycle for response evaluation. BM aspirate or biopsy will be performed at screening then at the end of Cycles 2, 4, and 6 (Day 1 of Cycles 3, 5, and 7) unless PB shows persistence of leukemic blasts that excludes the possibility of a marrow response. After Cycle 6 BM assessment (Day 1 of Cycle 7), BM aspirate/biopsy will be repeated every 3 months for the first year on study and then every 6 months thereafter until PB or BM assessment shows disease progression or relapse.

CR will be assessed by modified IWG 2003 AML Response Criteria (see Section 11.6), based on blood sampling and BM aspirate/biopsy. Response assessment will be based on BM blinded review and the most concomitant PB counts. After blinded BM response is confirmed, assessment of normal count recovery will be done based initially on the most concomitant PB counts and in later cycles on PB counts from Day 1 of each cycle to avoid transient treatment-induced normal count suppression. The central pathologist who evaluates BM and PB counts for response assessment, as well as the central response reviewer, will be blinded to treatment assignment (Section 6.2).

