11.6.1 Criteria for Response Assessment

Modified IWG 2003 Response Criteria (Table 18) will be used by an independent blinded reader to identify AML subjects with CR, CRp, CRi, or partial response. BM biopsy/aspirate and corresponding concomitant PB counts will be assessed by a blinded central pathologist, and all assessments of response will be reviewed and confirmed by an independent blinded central reviewer (either the same person who assessed pathology or a different blinded independent reviewer).

Table 18: Modified 2003 IWG AML Response Criteria

Response ^a	Peripheral Blood (PB)	Bone Marrow (BM)
CR	ANC \geq 1000/ μ L, Platelets \geq 100,000/ μ L, independence from RBC and platelet transfusions over the past week, no leukemic blasts ^b	<5% leukemic blasts
CRp	ANC \geq 1000/ μ L, Platelets <100,000/ μ L, independence from RBC transfusions over the past week, no leukemic blasts ^b	<5% leukemic blasts
CRi	ANC <1000/ μ L, no leukemic blasts ^b	<5% leukemic blasts
Partial response	ANC \geq 1000/ μ L, Platelets \geq 100,000/ μ L, no leukemic blasts ^b	Decrease of \geq 50% in leukemic blasts to level of 5% to 25%

^a Responses are based on both PB and BM conditions.

^b For the purpose of response assessment and according to published IWG criteria, blasts may be seen in PB as rare PB blasts may be identified during regeneration, but the subject is in CR if BM blasts are <5% with no Auer rods (Cheson et al 2003).

ANC=absolute neutrophil count; CR=complete response; CRp=complete response with incomplete platelet recovery; CRi=CR with incomplete blood count recovery.

Source: Cheson et al 2003

Subjects with these different response categories, as well as nonresponders and nonevaluable subjects described below, will be listed and summarized. In particular, best response will be used when a subject experienced different response levels at different visits. Response rate will be calculated for best response categories described below to assess overall efficacy observed.

- CR, CRp, CRi, partial response.
- Composite CR ($CR_c = CR + CR_p + CR_i$).

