Subjects who did not have a post-treatment efficacy assessment (ie, no BM or PB assessment) will be classified as nonevaluable for response presentations. These subjects will be included in the denominator of the ITT analysis for calculation of different response rates. Subjects who cannot be classified into a response category (CR, CRp, CRi, partial response) or the nonevaluable category will be classified as nonresponders.

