#### 7.3.4 Composite CR

The CRc rate is calculated as the number of subjects with a best response of CR, CRp, or CRi divided by the total number of subjects included in the efficacy analysis. The CRc rate will be compared between the 2 treatment groups using a Cochran Mantel-Haenszel test with the stratification variables the same as for CR and OS. If CR rate analysis and OS analysis are both significant, the CRc rate will be tested at an alpha level of 0.05; with a nonsignificant CR rate result ( $p > 0.04$ ) and a significant OS result at the 0.01 level, the CRc rate will be tested at an alpha level of 0.01 (see Section 7.3.7). In addition, the 2-sided 95% (or 99%, as appropriate) CI for the Mantel-Haenszel weighted difference in CRc rate between the 2 treatment groups will be provided.

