### 7.3.7 Test Sequence and Procedures of Statistical Tests for Efficacy Endpoints

To control the alpha errors associated with testing the multiple endpoints of CR rate, OS, CRc rate, NDAOH, and PFS, the following test sequence and procedures will be followed, assuming that the study continues after the planned interim analysis.

The primary efficacy variable CR rate will be tested first in the sequence at an alpha level of 0.04. A positive CR analysis ( $p \leq 0.04$ ) serves as a gatekeeper (Westfall and Krishen 2001) for the subsequent analyses. If the test for CR is positive (ie,  $p \leq 0.04$ ), then hierarchical analyses will be conducted at the 0.05 alpha level for the efficacy variables OS, CRc rate, NDAOH, and PFS (in that order). If the test for CR is not significant at the 0.04 level, then hierarchical analyses will be conducted at the 0.01 level for the efficacy variables OS, CRc, NDAOH, and PFS. The hierarchical test order and alpha value to be used for each test at the primary analysis time point are further described in Figure 2.

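### The response table is inconsistent in ANC: after a recent transfusion, a clear marrow is CRi below 1000/µL but can be nonresponse at or above it, so CRc may be misclassified in an unknown direction

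*SAP*

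**What the plan says.** SAP 7.3.1 (Table 1) and Protocol 11.6.1 (Table 18) give the same four rows.

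- **CR:** ANC at least 1000/µL, platelets at least 100,000/µL, marrow blasts under 5%, and "independence from RBC and platelet transfusions over the past week, no leukemic blasts".
- **CRp:** ANC at least 1000/µL, platelets under 100,000/µL, marrow blasts under 5%, and "independence from RBC transfusions over the past week, no leukemic blasts". Platelet transfusion is not mentioned.
- **CRi:** ANC under 1000/µL, no leukemic blood blasts, marrow blasts under 5%. There is no platelet or transfusion condition.
- **PR:** requires 5% to 25% marrow blasts, so it cannot take in a clear marrow.

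Both documents send everything else that is evaluable to nonresponse. The SAP sentence is "Subjects who cannot be classified into a response category (CR, CRp, CRi, PR) or the NE category will be classified as NR"; the protocol's is "Subjects who cannot be classified into a response category (CR, CRp, CRi, partial response) or the nonevaluable category will be classified as nonresponders".

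Two rules soften this. Across visits, "the best response in the order of CR, CRp, CRi and PR will be used when a subject experienced different response levels". Under Protocol 9.2, once a marrow response is confirmed, count recovery is judged first on the nearest blood sample and "in later cycles on PB counts from Day 1 of each cycle to avoid transient treatment-induced normal count suppression".

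CRc is formally tested. If CR is significant, SAP 7.3.7 states that "hierarchical analyses will be conducted at the 0.05 alpha level for the efficacy variables OS, CRc rate, NDAOH, and PFS (in that order"). If CR is not significant but OS is at 0.01, SAP 7.3.4 says "the CRc rate will be tested at an alpha level of 0.01 (see Section 7.3.7").

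**The concern.** A response scale should not give a worse label when one count improves and everything else stays the same. This one does. Among marrow-clear subjects with a recent transfusion, low neutrophils earn CRi and recovered neutrophils can earn NR. The cause is an asymmetry: CR and CRp carry transfusion conditions, CRi carries none, and the default absorbs what is left.

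At stake is CRc, the first endpoint tested after OS and the gate to NDAOH and PFS. The label also selects the progression rule in SAP 7.3.6. Subjects with CR, CRi or CRp progress on confirmed reappearance of blood blasts or on 5% or more marrow blasts. All others progress on a continued blast increase that calls for another therapy. The SAP counts the start of alternative anti-leukemia therapy as a PFS event for everyone, which narrows that second effect.

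**Working it through.** **1. The plan's own figure.** SAP 4.0 and Protocol 11.1 give CR 0.20 vs 0.30, n = 400 per arm, two-sided alpha 0.04 and about 89% power. Using the unstratified two-proportion formula with pooled null variance:

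power = Φ{[Δ√n − z√(2p̄q̄)] / √(p₁q₁ + p₂q₂)}

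Here Δ√n = 0.10 × 20 = 2.000, z = 2.054, √(2 × 0.25 × 0.75) = 0.612 and √(0.16 + 0.21) = 0.608. The result is Φ(1.22) = 0.889, which matches. The documents state no power for CRc.

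**2. Enumeration.** Fix marrow blasts under 5% and no leukemic blood blasts. Transfusions are those of the past week.

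| Platelets (/µL) | RBC transf. | Platelet transf. | ANC ≥1000 | ANC <1000 |
|---|---|---|---|---|
| ≥100,000 | no | no | CR | CRi |
| ≥100,000 | no | yes | no row: NR | CRi |
| ≥100,000 | yes | no | no row: NR | CRi |
| ≥100,000 | yes | yes | no row: NR | CRi |
| <100,000 | no | no | CRp | CRi |
| <100,000 | no | yes | CRp | CRi |
| <100,000 | yes | no | no row: NR | CRi |
| <100,000 | yes | yes | no row: NR | CRi |

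The totals are 1 CR + 2 CRp + 8 CRi + 5 unmatched = 16. Reading across, 5 of the 8 pairs get worse as ANC rises. These are the four with an RBC transfusion, and the one with only a platelet transfusion at platelets ≥100,000. The five are not NE, because a valid sample exists. Footnote b concerns rare blood blasts and does not waive the transfusion conditions.

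**3. Two consistent repairs.**

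- (a) CRi takes every marrow-clear profile that is not CR or CRp: 8 + 5 = 13 CRi cells and none unmatched. Relative to this rule, the current table undercounts CRc.
- (b) CRi carries the transfusion conditions of the CR and CRp rows: no RBC transfusion, and no platelet transfusion when platelets are ≥100,000. That leaves 3 CRi cells and 5 + 5 = 10 NR. Relative to this rule, the current table overcounts CRc.

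Both remove the inversion in ANC. Rule (b) leaves one in platelets: at ANC ≥1000 with only a platelet transfusion, platelets <100,000 is CRp and ≥100,000 is NR. Under (a) both profiles count toward CRc.

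**4. Who is affected.** Because best response is used, the current wording loses a subject from CRc only if some visit falls in the five cells and no visit meets CR, CRp or CRi. One marrow-clear assessment with ANC under 1000 is enough to rescue the subject.

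**5. Illustration, direction (a) only.** Assumed: 400 per arm; TC CRc 28% (top of the 11% to 28% range in SAP 1.3); guadecitabine CRc 38% (not in the documents); and a share of CRc responders missed, equal in both arms. Each rate is multiplied by (1 − share).

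| Share missed | Rates | Power, alpha 0.05 | Power, alpha 0.01 |
|---|---|---|---|
| 0% | 28.0% vs 38.0% | 85.4% | 66.8% |
| 5% | 26.6% vs 36.1% | 82.7% | 62.6% |
| 10% | 25.2% vs 34.2% | 79.7% | 58.3% |
| 20% | 22.4% vs 30.4% | 72.9% | 49.6% |

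A 10% share is 0.10 × 112 = 11.2 TC subjects and 0.10 × 152 = 15.2 guadecitabine subjects. With unequal shares the result can move either way at alpha 0.05: TC 5% and guadecitabine 10% gives 64.7%; the reverse gives 91.8%.

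At 28% vs 55% (Phase 2 rate, Protocol Table 3), power stays at least 99.9% at both alphas for equal shares up to 20%. The same holds at 28% vs 57% (SAP 1.3).

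**The case against.** The strongest reply is that the plan is not silent. The default assigns these visits to NR in both documents, so the analysis can be run as written, and the sponsor may have meant it. The first half stands: this is not missing text. The second half does not rescue the table, because no reason is given why the same transfusion should count against a subject only once neutrophils recover.

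A reader might infer that CRc is undercounted and CRi should simply be widened. The documents do not support that. Adding a transfusion condition to CRi closes the asymmetry equally well, and on that view CRc is now overcounted. Which rule matches the modified criteria depends on the sponsor's intent, which neither document states.

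A reader might also take the power table as a loss to the trial. It is not evidence of one. The 38% and the shares are invented. The 28% is an observed rate from other trials, already net of whatever their criteria excluded. No planned CRc power exists to be eroded.

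The objection that the reach is narrow also stands. CR and OS are untouched, CRc is tested only after OS succeeds, and best response with later re-reading of counts will rescue some subjects.

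**Conclusion.** The concern holds as a minor defect: CRc classification is non-monotone in ANC, with 5 of 8 otherwise identical profile pairs reversed. That part follows directly from the table and needs no assumption. CRc, and through it the gate to NDAOH and PFS, may be misclassified. The number of subjects, the balance between arms and the sign of the error cannot be obtained from the documents.

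The co-primary CR rate, OS and the stated 89% power are unaffected, since the five profiles fail CR in any case. The CRc power figures are illustration only. At rates like those in Phase 2 the loss is negligible, and it would matter only if the true CRc difference were much smaller.

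**What to change.** Before the CRc analysis, adopt one consistent definition of CRi for CRc, leaving the CR row unchanged:

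- (a) CRi covers every remaining subject with under 5% marrow blasts and no leukemic blood blasts (footnote b applying) who does not meet CR or CRp; or
- (b) CRi carries a transfusion condition consistent with the CR and CRp rows. In that case, also say whether the remaining platelet inversion is intended.

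The sponsor should state which rule matches its modified criteria, then run CRc under the other rule and under the current wording as sensitivity analyses. The same definition should go to the blinded reader and to the investigators, whose assessments SAP 7.3.1 lists using the same table. SAP Table 1 and Protocol Table 18 should be reconciled so that they do not diverge on a tested endpoint.

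State in SAP 7.3.6 that this label selects the progression rule, and repeat PFS under the current wording. Protocol 7.3.1 uses CRi and CRp in its dosing text; the sponsor must reconcile those passages with the analysis definition. No dosing change is proposed here.

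Cost: one definition, matching reader and investigator instructions, alignment of two tables and a few sensitivity analyses. No new data are needed, because the CR and CRp rows already require the counts and transfusion history. The downside is that CRi and CRc counts, and some PFS dates, may shift slightly.

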- Slides should be Wright Giemsa or May Grunwald Giemsa stained. Send 1 or 2 PB and BM slides for each subject at each time point. Detailed instructions on collection, labeling and shipping are described in the Study Lab Manual. A BM sample adequate for analysis must be obtained. Repeat the BM sample if not interpretable.
- Response assessment is done on Day 1 of Cycles ≥ 2 based on BM aspirate/biopsy and the most concomitant PB. Assess PB at screening and on Day 1 of each cycle. Perform BM aspirate/biopsy at screening and then at the end of Cycles 2, 4, and 6 (ie, Day 1 of Cycles 3, 5, and 7 [± 7 -day window]) unless PB shows persistence of leukemic blasts that excludes the possibility of a marrow response. After blinded BM response is confirmed, assessment of normal count recovery is done based initially on the most concomitant PB counts and in later cycles on PB counts from Day 1 of each cycle to avoid transient treatment-induced normal count suppression. Subjects who discontinue treatment before Cycle 6 Day 1 before documented disease progression must undergo response assessment until disease progression or relapse is confirmed. After Cycle 6,

repeat BM aspirate/biopsy every 3 months for the first year on study and then every 6 months thereafter until PB or BM assessment shows disease progression or relapse. Refer to Section 9.2.

- q. **Hospitalizations/Transfusions:** Document all blood and platelet transfusions (blood product transfused and units) within 28 days before starting study treatment. Document all hospital admission and discharge dates and main reason for hospitalization, as well as all blood and platelet transfusions (blood product transfused and units), from Cycle 1 Day 1 and then monthly to 6 months after the first dose or to the Tx Dsc Safety FU visit, whichever is later. Not required for visits every 3 months in long-term follow-up.
- r. **Disease progression status:** For subjects who discontinue study treatment before disease progression is documented, PB and BM aspirate/biopsy assessments as described in footnote “p” should continue until disease progression or relapse is confirmed.

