### 7.3.2 Complete Response

The primary endpoint of CR rate will be calculated as the number of subjects with a best response of CR divided by the total number of subjects included in the efficacy analysis. The CR rate will be compared between the 2 treatment groups using a Cochran Mantel-Haenszel test at an alpha level of 0.04 stratified by the stratification factors used at randomization: age (<75 or ≥75 years), ECOG performance status (0-1, 2-3), study center region (North America, Europe, ROW), and secondary AML (secondary to MDS or other antecedent hematologic disorder) or poor-risk cytogenetics (Yes, No/Unknown). The null and alternative hypotheses are:

- **Null hypothesis  $H_0$ :** CR rates are the same between the guadecitabine treatment and TC treatment
- **Alternative hypothesis  $H_1$ :** CR rates are different between the two treatment arms

A 2-sided  $p$  value of  $\leq 0.04$  will be judged as statistically significant. In addition, a normal approximated, two-sided 96% CI for the (Mantel-Haenszel weighted) difference in CR rates between guadecitabine treatment and TC treatment will be provided (Koch et al 1990).

The following sensitivity analyses will be conducted for the co-primary endpoint of CR rate for evaluating robustness of the treatment effect:

- 1) The CR rate will be compared between the guadecitabine and TC using a regular Chi-square test without stratification.
- 2) A logistic regression analysis will be performed for the primary endpoint of CR with treatment group (guadecitabine or TC), age (<75 or ≥75 years old), ECOG performance status (0-1, 2-3), the geographic region (North America, Europe, ROW) of the study centers, and secondary AML or poor-risk cytogenetics (Yes, No/Unknown) as fixed factors. The point estimate and 95% CI, as well as the  $p$  value will be provided for the odds ratio (OR) comparing the odds of being a responder in guadecitabine treatment with the odds of being a responder in TC treatment.
- 3) An "as-treated" analysis will be conducted on the CR rate, based on treatment actually received as described in Section 5.3, using the same Cochran Mantel-Haenszel test and same

stratification variables described above. Subjects who were randomized but not treated will not be included in this analysis.

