### 7.3.6 Progression-free Survival

Progression is defined as the earliest occurrence of one of the following:

- For subjects with CR, CRi, or CRp, the confirmed (at least 2 PB samples at least 1 week apart) appearance of leukemic blasts in PB by investigator or central assessment, OR  $\geq 5\%$  leukemic blasts in the BM by blinded central pathologist assessment.
- For all other subjects, when PB or BM shows evidence of continued increase in blasts % that necessitates alternative therapy.
- Death.

PFS is defined as the number of days from randomization to the earliest date of investigator's assessment of disease progression, subject receives an alternative anti-leukemia therapy, or relapse by PB assessment or blinded BM assessment, whichever occurs first, or death (regardless of cause). PFS time will be censored on the last date the subject is known to be alive without a relapse/disease progression.

$$\text{PFS in days} = (\text{earliest date of progression, relapse, alternative anti-leukemia therapy, death or censoring} - \text{date of randomization})$$

PFS will be compared between the 2 treatment groups using a stratified log-rank test (by the same stratification factors as used at randomization) at an alpha level of 0.05, or 0.01, as appropriate, if CRc and NDAOH test results are significant at that required level (see

[figure not shown]
Section 7.3.7). The median (and quartiles) duration of PFS and the associated 95% CI for each treatment arm will be estimated using the Kaplan-Meier method. In addition, the HR and its 95% CI will be estimated using a Cox proportional-hazard model with treatment group as the independent variable and stratified by the same randomization stratification factors as used for the log-rank test. In a supportive analysis, the assumption of proportional hazards will be evaluated to assist interpretation of the Cox regression analysis results.

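### Best response of CR has no cut-off at the start of other anti-leukemia therapy, so by a few remaining routes a CR reached on later treatment or after transplant can count in the co-primary endpoint.

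*SAP*

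**What the plan says.** SAP 7.3.2 defines the co-primary CR rate as the "number of subjects with a best response of CR divided by the total number of subjects included in the efficacy analysis". SAP 7.3.1 fixes what best response means: "the best response in the order of CR, CRp, CRi and PR will be used when a subject experienced different response levels at different visits". Protocol 11.6.1 and 11.6.2 define it the same way. No time window is given, and no cut-off at other anti-leukemia therapy or hematopoietic cell transplant (HCT).

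The next sentence of SAP 7.3.1 sets one limit. Subjects who progressed "without first having a response (CR, CRp, CRi, or PR) will be included in the NR category for summary purpose". For subjects without CR, CRi or CRp, SAP 7.3.6 defines progression as the point "when PB or BM shows evidence of continued increase in blasts % that necessitates alternative therapy".

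Assessment goes on after study treatment ends. Footnote p to the schedule of events (protocol 9.5.1) says: "Subjects who discontinue treatment before Cycle 6 Day 1 before documented disease progression must undergo response assessment until disease progression or relapse is confirmed". Footnote r and protocol 9.5.5 and 9.5.6 extend this to subjects who stop at any time without documented progression. The end point is progression or relapse, not the start of a new therapy. The regimen and start date of subsequent therapy are recorded (protocol 9.5.5, 9.5.6).

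Other endpoints do deal with new therapy. SAP 7.3.6 lists "subject receives an alternative anti-leukemia therapy" among the PFS events, and sensitivity analysis 3 in SAP 7.3.3 censors OS at other therapy, naming HCT. None of the five CR sensitivity analyses in SAP 7.3.2 mentions it.

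**The concern.** A response rate is normally read as the effect of the assigned treatment. Without a cut-off, the rule can credit the randomized arm with a CR that a later drug or a transplant produced. Blinded central reading does not prevent this, because nothing tells the reader or the programmer to set aside samples taken after a switch.

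The endpoint carries weight. CR is tested at 0.04 and can make the study positive on its own (SAP 7.3). A significant CR result also raises the level for OS and the ranked secondary endpoints from 0.01 to 0.05 (SAP 7.3.7). The trial is open-label, so the frequency and timing of switching may differ between arms, and the CR difference could shift in either direction.

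**Working it through.** **Step 1: which routes are open.** Setting SAP 7.3.1, SAP 7.3.6 and the protocol follow-up rules side by side:

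- *Progression with no earlier response, then a CR on later therapy:* scored NR, so not counted. SAP 7.3.3 (sensitivity analysis 3) says other therapies usually start at progression, so this is the commonest route.
- *(i) PR, CRi or CRp, then HCT or other therapy, then CR:* open. The same SAP text says HCT goes to subjects whose disease is well controlled, and the NR rule does not cover them.
- *(ii) Study treatment stopped without progression (for example for toxicity), a switch, then CR:* open. Starting a therapy is a PFS event but is not in the list that defines progression.
- *(iii) PR, CRi or CRp, then progression, then CR on later therapy:* open on the literal text, because the NR rule applies only where no response came first.

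**Step 2: reproduce the planned power.** Inputs from SAP 4.0: n = 400 per arm, p1 = 0.20, p2 = 0.30, two-sided alpha 0.04 (z = 2.0537). I used the normal approximation for two proportions, unstratified, as an approximation to the stratified test:

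power = Φ((d − z·s0)/s1), with s0 = √(2p̄(1−p̄)/n) and s1 = √(p1(1−p1)/n + p2(1−p2)/n).

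Here d = 0.10, p̄ = 0.25, s0 = √(2 × 0.25 × 0.75/400) = 0.03062 and s1 = √((0.16 + 0.21)/400) = 0.03041. Then (0.10 − 2.0537 × 0.03062)/0.03041 = 1.220 and Φ(1.220) = 88.9%. The stated 89% is reproduced, and no planned figure is in dispute.

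**Step 3: add assumed later-therapy CRs.** One point is 0.01 × 400 = 4 subjects in an arm. The documents give no rate, so one and two points are assumptions. The formula is the same.

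| Scenario | CR rates (TC v guadecitabine) | Result |
|---|---|---|
| No extra CRs | 0.20 v 0.30 | power 88.9% |
| +1 point, both arms | 0.21 v 0.31 | power 88.1% |
| +2 points, both arms | 0.22 v 0.32 | power 87.3% |
| +1 point, TC only | 0.21 v 0.30 | power 80.8% |
| +2 points, TC only | 0.22 v 0.30 | power 70.1% |
| No true difference, no extra CRs | 0.20 v 0.20 | false win 2.0% |
| No true difference, +1 point in guadecitabine only | 0.20 v 0.21 | false win 4.4% |
| No true difference, +2 points in guadecitabine only | 0.20 v 0.22 | false win 8.7% |

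A false win is rejection in favor of guadecitabine, nominally half of 0.04. If the extra CRs are instead set as the same share of non-CR subjects in each arm, 1% gives 0.208 v 0.307 and 87.6%, and 2% gives 0.216 v 0.314 and 86.3%.

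**Step 4: could the pool for route (i) differ by arm?** Protocol Table 3 shows CRi without CR in 11 of 51 phase 2 subjects (22%). From protocol Table 9, CRc minus CR is (67 − 38)/242 = 12% for decitabine, (67 − 48)/241 = 8% for azacitidine and (24 − 17)/215 = 3% for low-dose cytarabine. These are cross-trial figures, and they describe who could convert, not how many would. They make an imbalance conceivable but do not establish one.

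**The case against.** The strongest reply is that the plan already blocks most of the problem. A reader might infer that any subject who fails study drug, switches and then responds becomes a CR responder. The documents do not support that, because a nonresponder whose rising blasts call for other therapy has progressed and is scored NR. This point stands and narrows the concern to the three routes above. The NR sentence is limited to summary purposes, which leaves slight doubt, but the same best-response categories feed the CR rate.

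A reader might also infer that the plan deliberately counts later-therapy CRs. It does not say so. The count follows from silence on a cut-off combined with continued assessment.

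Opportunities are also limited. Off-treatment follow-up may be hematology alone or a telephone contact (protocol 9.5.6), whereas CR needs a centrally read marrow with concomitant counts. Other anticancer therapy is barred during study treatment (protocol 7.5.2), and TC subjects may not move to SGI-110 (protocol 7.2). These facts reduce the number of such CRs but do not bring it to zero.

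Counting outcomes whatever therapy follows is a legitimate ITT choice, and the main OS analysis makes it. For CR, though, neither document states that choice.

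Last, a cut-off is not neutral. Open-label investigators set its date, and protocol 7.1.2 reports late responses (of 51 subjects, 2 responded and 2 improved to CR after more than 6 cycles). Those responses came with continued SGI-110, so a cut-off at other therapy would keep CRs of that kind. The dependence on switching remains a real cost.

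**Conclusion.** The point holds in limited form. Best response has no cut-off at other anti-leukemia therapy, and a later-therapy CR can enter the co-primary count by routes (i) to (iii).

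The size is unknown. If the extra CRs fall equally on both arms, the loss is small: power of 88.1-87.3% for one to two points, against 88.9%. The effect matters only if they fall mainly on one arm: power of 80.8-70.1% if in TC, or a false-win chance of 4.4-8.7% against 2% if in guadecitabine with no true difference. These figures rest on the plan's 0.20 and 0.30 as CR rates before any other therapy, on 400 per arm, and on assumed excesses. A reader might take the one-arm scenarios as forecasts of bias in a given direction, but nothing in the documents supports either the imbalance or its direction.

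This is a cheap improvement rather than a flaw that undermines the design.

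**What to change.** Add to SAP 7.3.1 and 7.3.2: for CR and CRc, only responses documented on or before the start date of the first other anti-leukemia therapy, including HCT, are counted. Later assessments are disregarded, and the subject keeps the best response reached up to that date and stays in the ITT denominator. Report the any-time CR rate, with the same stratified test, as a further sensitivity analysis in SAP 7.3.2.

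The cost is one sentence, one date comparison in programming and one extra table, using dates already collected. N stays at 800, and planned power is unchanged if 0.20 and 0.30 are read as rates before other therapy. The downside is that a few late CRs are no longer counted and the cut-off date depends on open-label switching. The any-time analysis makes both visible. The wording should be fixed before the final analysis, because the sponsor is not blinded.
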